5. INVESTIGATIONAL PRODUCT (TREATMENT, DEVICE) AND INDICATION

5.1 PRECLINICAL EVIDENCE

Moderna's bivalent mRNA-1273.214 vaccine showed a potent neutralizing antibody response against variants that are being monitored such as alpha, beta, gamma, delta and the variant of concern omicron when compared to their approved monovalent vaccine mRNA-1273 Spikevax (6). Similarly, Pfizer-BioNTech has developed a bivalent mRNA vaccine (Wuhan/Omicron BA.1) with promising results (7).

5.2 CLINICAL EVIDENCE TO DATE

In a phase 2–3 study, Moderna compared the 50-µg bivalent vaccine mRNA-1273.214 (25 µg each of ancestral Wuhan-Hu-1 and omicron B.1.1.529 [BA.1] spike messenger RNAs) with their previously authorized 50-µg mRNA-1273 booster among adults who received a two-dose (100-µg) primary series and first booster (50-µg) dose of mRNA-1273 (\geq 3 months earlier) (6). "In participants with no previous SARS-CoV-2 infection, the geometric mean titers (GMT) of neutralizing antibodies against the omicron BA.1 variant were 2372.4 (95% confidence interval [CI], 2070.6 to 2718.2) after receipt of the mRNA-1273.214 booster and 1473.5 (95% CI, 1270.8 to 1708.4) after receipt of the mRNA-1273 booster. In addition, 50-µg mRNA-1273.214 and 50-µg mRNA-1273 elicited GMT of 727.4 (95% CI, 632.8 to 836.1) and 492.1 (95% CI, 431.1 to 561.9), respectively, against omicron BA.4 and BA.5 (BA.4/5), and the mRNA-1273.214 booster also elicited higher binding antibody responses against multiple other variants (alpha, beta, gamma, and delta) than the mRNA-1273 booster. Safety and reactogenicity were similar with the two booster vaccines." (6).

No peer-reviewed publication is currently available for the bivalent SARS-CoV-2 vaccine from Pfizer-BiNTech (19. September 2022) . Hence we cite from the available press releases (7, 8). "Pfizer/BioNTech's bivalent vaccine contains 15-µg of mRNA encoding the wild-type spike protein of SARS-CoV-2, which is present in the Original Pfizer-BioNTech COVID-19 Vaccine, and 15-µg of mRNA encoding the spike protein of the Omicron BA.4/BA.5 subvariants." (8). Pfizers' Omicron-adapted vaccine candidates (30 µg and 60 µg) studied in the Phase 2/3 trial in 1,234 participants 56 years of age and older elicited substantially higher neutralizing antibody responses against Omicron BA.1 when compared to the companies' current COVID-19 vaccine (7). "The pre-specified criterion for superiority was measured by the ratio of neutralizing geometric mean titers (GMR) with the lower bound of the 95% confidence interval >1. The geometric mean ratio for the bivalent 30 µg and 60 µg vaccines compared to the current COVID-19 vaccine were 1.56 (95% CI: 1.17, 2.08) and 1.97 (95% CI: 1.45, 2.68), respectively" (7). One month after administration, a booster dose of the Omicron-adapted bivalent candidates (30 µg and 60 µg) conferred a 9.1 and 10.9-fold increase in neutralizing GMTs against Omicron BA.1. The vaccine candidates were well-tolerated in participants who received one or the other Omicron-adapted vaccine. In addition, "a SARS-CoV-2 live virus neutralization assay tested on sera from participants over 56 years of age and older, sera efficiently neutralized BA.4/BA.5 with titers approximately 3-fold lower than BA.1" (7).

There is no evidence on the efficacy and safety of these bivalent mRNA vaccines in immunocompromised people.

5.3 RISKS / BENEFITS

Participants gain information on their immune status following booster vaccination over time (at 4 weeks, 8 weeks, and 6 months). This knowledge can be important to participants and treating physicians when new boosters might be considered. There are only minimal risks associated with the sampling of blood (12). The study population frequently requires drawing of blood and the study samples can be drawn in the context of other routine blood examinations avoiding any additional risk. Results such as immune response of the patients obtained by the analysis of the blood samples will be communicated to the participant. By taking part in this study the participant will help benefit future patients by adding to the knowledge for this particular population and potentially improving vaccination

strategies.

5.4 JUSTIFICATION OF CHOICE OF STUDY POPULATION

According to the Swiss Federal Office of Public Health immunocompromised patients are of high priority of vaccinations and further research is needed to understand their response to vaccines appropriately. The treating physicians of the STCS and the SHCS will administer the vaccines according to the latest vaccine recommendations (13).

6. STUDY OBJECTIVES

6.1 OVERALL OBJECTIVE

Overall Objective Scenario 1: To compare immunologic response and safety of the bivalent mRNA-1273.214 vaccine from Moderna among immunocompromised persons (persons living with HIV or kidney or lung transplant recipients) to the immunologic response of immunocompromised persons who received the bivalent mRNA vaccine from Pfizer-BioNTech.

Overall Objective Scenario 2: To assess immunologic response and safety of the bivalent mRNA-1273.214 vaccine among immunocompromised persons (persons living with HIV or kidney or lung transplant recipients).

6.2 OBJECTIVES RELATED TO A PLATFORM BASED NESTED EXTENSION STUDY TO INVESTIGATE THE IMMUNOLOGIC RESPONSE AND SAFETY OF THE CURRENT BIVALENT MRNA VACCINES

- To assess the efficacy of the bivalent mRNA vaccines
- To evaluate the durability of the bivalent mRNA vaccine response: Proportion of participants that show waning of antibody response at 8 weeks and 6 months, respectively, measured by pan-IgG antibodies
- To describe the longitudinal T-cell immune response of the bivalent mRNA vaccines in a sub-sample of participants: cellular immune response build up and waning
- To assess the safety of the bivalent mRNA vaccines

6.3 SAFETY OBJECTIVES

We aim to systematically assess vaccine-related adverse events until 4 weeks after vaccination and serious adverse events over the entire study period.

If a serious event occurs, defined as a serious complication during a blood draw, the research project will be interrupted and the Ethics Committee notified on the circumstances via BASEC within 7 days according to HRO Art. 21^{1.}

¹ A serious event is defined as any adverse event where it cannot be excluded, that the event is attributable to the sampling of biological material or the collection of health-related personal data, and which: a. requires inpatient treatment not envisaged in the protocol or extends a current hospital stay;

b. results in permanent or significant incapacity or disability; or

We aim to systematically assess vaccine-related adverse events until 4 weeks after vaccination and serious adverse events over the entire study period

6.4 STUDY OUTCOMES

6.4.1 Immunological Outcomes

Immunological endpoints:

- The proportion of patients with a positive antibody response to SARS-CoV-2 spike (S1) protein receptor binding domain in human serum or plasma assessed by the commercial immunoassay Elecsys Anti-SARS-CoV-2 S (Elecsys S) from Roche(1) 4 weeks, 8 weeks, and 6 months after vaccination. An antibody response will be considered to be still sufficient, using the threshold ≥100 units/ml, predicting a protective immune response as indicated by Hall et al.(2), and Khoury and colleagues.(3)
- Geometric mean of quantitative antibodies against RBD at 4 weeks, 8 weeks, and 6 months using Elecsys S test from Roche.
- The proportion of patients with a positive antibody response using SARS-CoV-2 spike (S1) Elecsys S by Roche, using a threshold of ≥0.8 units/ml as defined by the manufacturer at 4 weeks, 8 weeks, and 6 months.
- T-Cell response, using a commercially available IFN-γ release assay (Quant-T-Cell SARS-CoV-2 by Euroimmun and Elecsys® IGRA SARS-CoV-2 by Roche) in a subsample of 60 patients (40 receiving bivalent (Wuhan/BA.1) SARS-CoV-2 mRNA-1273.214 vaccine by Moderna; 20 receiving bivalent (Wuhan/BA.1) SARS-CoV-2 mRNA vaccine by Pfizer-BioNTech) 4 weeks and 6 months after vaccination (sub-sample will be decreased to 40 patients in Scenario 2).

6.4.2 Clinical Outcomes

Clinical Endpoints:

- Newly confirmed SARS-CoV-2 infections 4 weeks, 8 weeks, and 6 months after vaccination.
- Newly confirmed symptomatic SARS-CoV-2 infection 4 weeks, 8 weeks, and 6 months after vaccination
- Severe COVID-19 infections (requiring hospitalization or leading to death) 4 weeks, 8 weeks, and 6 months after vaccination

6.4.3 Other Outcomes of Interest

None.

6.4.4 Safety Outcomes

Safety Endpoints:

- Vaccine-related adverse events 4 weeks after vaccination
- Serious adverse events 4 weeks, 8 weeks, and 6 months after vaccination

c. is life-threatening or results in death.

7. STUDY DESIGN

7.1 GENERAL STUDY DESIGN AND JUSTIFICATION OF DESIGN

Nested within the Swiss HIV Cohort study (SHCS) (14) and the Swiss Transplant Cohort Study (STCS)(15) we have set-up the COrona VaccinE tRiAL pLatform (COVERALL; see also master-protocol and first sub-protocol). This trial platform allowed for rapid patient recruitment, efficient and cost-saving data collection, as well as high flexibility in adapting the study design, which is key given the rapid changing circumstances during the COVID-19 pandemic. The platform set-up and a first pilot trial (first sub-protocol) were supported by a competitive grant from the Swiss National Science Foundation (4).

Within the established trial platform we conducted a first multicentre randomised controlled, open-label, 2-arm randomised controlled trial (**first sub-protocol**) in immunocompromised patients to assess the efficacy of the two mRNA SARS-CoV-2 vaccines (i.e. BNT162b2 by Pfizer / BioNTech and mRNA-1273 by Moderna) that reached market authorisation in Switzerland. The primary clinical outcome was change in pan-lg antibody response (pan-lg anti-S1-RBD; baseline vs. 12 weeks after first vaccination; 8 weeks after second vaccination, respectively). We randomised a total of 430 patients (352 from SHCS and 78 from STCS). In a recently conducted observational extension (i.e. **second sub-protocol**), we assessed the non-inferiority of a third mRNA-1273 vaccination compared to a third BNT162b2 vaccination with respect to immune response (*manuscript in preparation*).

Within the here proposed substudy-3 (**third sub-protocol**) we aim to conduct an observational study to assess the antibody response in immunocompromised patients from the SHCS or the STCS after having received the new bivalent SARS-CoV-2 vaccine either from Moderna or Pfizer-BioNtech. We plan to assess the antibody response over time (i.e. at 4 weeks, 8 weeks and 6 months) to be able to assess the durability of the bivalent mRNAbooster vaccine response (16) in immunocompromised patients.

7.2 METHODS OF MINIMISING BIAS

7.2.1 Randomization

Not applicable in observational study

7.2.2 Blinding procedures

All personnel and patients will know which vaccine was given in clinical routine. Outcome assessors conducting laboratory analyses will not be aware which vaccine patients received.

7.2.3 Other methods of minimising bias

7.3 UNBLINDING PROCEDURES (CODE BREAK)

Not applicable.

7.4 STUDY POPULATION

This is a multi-centre study recruiting patients from 3 of the 7 study centres of the SHCS and 3 of the 6 study centres of the STCS (i.e. University Hospital Basel, University Hospital Zürich, Inselspital University Hospital Bern [only SHCS], and University Hospital Lausanne [CHUV; only STCS]). Both cohorts are representative for individuals living with HIV and solid organ transplants:

SHCS study centres:

- Department of Infectious Diseases, Inselspital University Hospital Bern, University of Bern
- Division of Infectious Diseases & Hospital Epidemiology, University Hospital Basel
- Division of Infectious Diseases and Hospital Epidemiology, University Hospital Zurich, University of Zurich

STCS study centres:

- Klinik für Pneumologie, Universitätsspital Zürich
- Klinik für Nephrologie, Universitätsspital Zürich
- Klinik für Pneumologie, Universitätsspital Basel
- Klinik für Transplantationsimmunologie & Nephrologie, Universitätsspital Basel
- Service de pneumologoie, Universitätsspital Lausanne (CHUV)
- Centre de transplantation d'organes, Universitätsspital Lausanne (CHUV)

The cohorts are described in more detail elsewhere (14, 15, 17, 18). The study will be explained to eligible patients during their visit at the cohort centre. Cohort patients will be contacted by phone or letter to inform them about the study.

Inclusion and exclusion criteria:

Inclusion criteria:

- Patients with either a HIV infection or recipients of solid organs registered in the SHCS and STCS cohorts and signed informed consent form
- Patients aged ≥18 years
- Patients receiving a new bivalent (Wuhan/Omicron BA.1) mRNA SARS-CoV-2 vaccine in the frame of clinical routine, according to the treating physician
- Provide consent for the COVERALL observational bivalent booster extension study (third subprotocol)

Exclusion criteria:

- Acute symptomatic SARS-CoV-2 infection, influenza or other acute respiratory tract infection
- Any emergency condition requiring immediate hospitalization for any condition
- Known allergy or contra-indications for vaccines or any vaccine components or any other contraindication to receive the vaccine according to the treating physician
- Patients who did not receiv the "baseic immunization" SARS-CoV-2 vaccination (e.g. two shots of Spikevax from Moderna, two shots of Comirnaty from Pfizer-BioNtech).

7.5 RECRUITMENT AND SCREENING

Patients recruitment from the SHCS or the STCS: Specific eligibility criteria can be defined and implemented by the trial platform data base which is based on all clinical and laboratory cohort data and managed by the cohort data centres. Both cohorts have developed a clinical information system that summarizes all relevant clinical and laboratory information for patients and widely serves as a clinical management and decision support system. Eligible patients can be flagged within this system. Treating cohort physicians will contact flagged patients either by letter, phone call, or during routine cohort study visits to inform and invite them in this study. Of note: only relatively few people living with HIV have CD4 cell counts below 350 cells/ μ L (<5%). Therefore local investigator will receive a list, highlighting these patients so that they can priories this patient group at the beginning of the study to ensure that we can reach the required sample size.

7.6 ASSIGNMENT TO STUDY GROUPS

Since this is an observational study extension, we will not do any active assignment. Participants will receive the bivalent vaccine which they are given during routine practice. We will implement monitoring reports so capture how many patients from which sub-group are already participating. When the required sample size is reached for a specific sub-group investigators will be informed to stop recruitment for this sub-group of patients.

7.7 CRITERIA FOR WITHDRAWAL / DISCONTINUATION OF PARTICIPANTS

We refer to the master protocol.

7.8 DATA COLLECTION AND FOLLOW-UP FOR WITHDRAWN PARTICIPANTS

Patients have the right to withdraw the planned follow-up visits. Clinical outcomes for those patients will be assessed from routinely collected cohort data.

7.9 TRIAL SPECIFIC PREVENTIVE MEASURES

All patients included into the trial-extension will continue all medication taken for the treatment of their chronic conditions. For transplanted patients with recent organ transplant receipt and / or more severe immune-suppressant treatment, decision to vaccinate patients and for trial participation is taken by the treating physicians by considering all benefit and potential harms for vaccination against Sars-CoV-2 in a particular patient.

Use of any drugs for the treatment of local or systemic adverse effects of vaccines is according to clinical judgement by clinicians.

7.10 CONCOMITANT INTERVENTIONS (TREATMENTS)

Concomitant drugs for patients included into the trial-extension are recorded within the routine cohort based data collection structure (see master protocol). Within substudy-3 we will systematically assess during all study visits the use of monoclonal antibodies and the flu vaccination (see case report form). Physicians are free in the choice of any concomitant drugs for the treatment of HIV, immunosuppressants for transplanted patients or any other drugs used for the treatment of additional chronic conditions and take decisions for their use according to best clinical judgement and treatment guidelines. There are no particular drugs that are not permitted for their use during vaccination and follow-up.

Use of any drugs for the treatment of local or systemic adverse effects of vaccines is according to clinical judgement by clinicians.

8. STUDY DRUG / MEDICAL DEVICE ACCOUNTABILITY

The vaccines will be administered in the frame of clinical routine at official vaccination centres. These can be located directly at University Hospitals or at other locations (e.g. Messehalle in Basel). We will collect blood at the baseline visit, at 4 weeks, 8 weeks and 6 months after vaccination.

9. RETURN OR DESTRUCTION OF STUDY DRUG / MEDICAL DEVICE

Does not apply, since the vaccines will not be given in the frame of the substudy-3.

10. STUDY ASSESSMENTS

Study flow chart(s) / table of study procedures and assessments

Study schedule

Assessment	Baseline	4 weeks	8 weeks	6 months
		(± 1 week)	(± 2 weeks)	(± 4 weeks)
Eligibility and consent ^a	Х			
Baseline assessment	Х			
Assessment of monoclonal antibody treatment and flu vaccination	Х	X	X	X
Vaccination (mRNA-1273.214 or product by Pfizer-BioNtech) in the frame of clinical routine ^b	Х			
Anti-SARS-CoV-2 S and N antibody tests (Elecsys® Roche)	Х	X	x	x
T-cell test (IFN-γ release assay): Quant-T-Cell SARS-CoV-2 by Euroimmun and Elecsys® IGRA SARS-CoV-2 by Roche	х	×		X
Only in sub-sample of 60 patients (Scenario 1) or 40 patients (Scenario 2)				
Clinical outcomes		Х	Х	х
Vaccine specific adverse events		Х		
Serious adverse events		Х	Х	х

^a Informed consent can also be given at later time point if bivalent vaccine was already administered in the frame of clinical routine and consent is only referring to blood samples and use of data.

^b Will be administered in the frame of clinical routine based on recommendation from treating physician

10.1 ASSESSMENTS OF OUTCOMES

10.1.1 Assessment of immunological endpoints

We will assess the proportion of patients with a positive antibody response to SARS-CoV-2 spike (S1) protein receptor binding domain in human serum or plasma assessed by the commercial immunoassay Elecsys Anti-SARS-CoV-2 S (Elecsys S) from Roche (1) 4 weeks, 8 weeks, and 6 months after vaccination. An antibody response will be considered to be still sufficient, using the threshold \geq 100 units/ml, predicting a protective immune response as indicated by Hall et al. (2), and Khoury and colleagues (3). We will also assess antibody response at baseline (i.e. before vaccination with bivalent SARS-CoV-2 vaccine). However, we assume that some patients may have received already the bivalent SARS-CoV-2 vaccine before the start of this study, hence we will not have a baseline blood sample from those patients. Furthermore we will measure the geometric mean of quantitative antibodies against RBD at 4 weeks, 8 weeks, and 6 months using Elecsys S test from Roche and the proportion of patients with a positive antibody response using SARS-CoV-2 spike (S1) Elecsys S by Roche, using a threshold of \geq 0.8 units/ml as defined by the manufacturer at 4 weeks, 8 weeks, and 6 months.

Therefore, a blood sample will be taken during each study visit (EDTA blood sample (1 x 3 ml)):

Participating centres can decide if they want to conduct Elecsys® Anti-SARS-CoV-2 N and S tests locally at their own routine laboratory, or if they want to send the blood samples in large batches for the analyses to the Institut für Medizinische Virologie (IMV), in Zürich

In a sub-sample of 40 patients who receive the bivalent mRNA SARS-CoV-2 vaccine from Moderna and 20 who receive bivalent vaccine from Pfizer-BioNTech, we will assess the T-Cell response using a commercially available IFN- γ release assay (Quant-T-Cell test by Euroimmun (19)) at baseline, 4 weeks and 6 months. We will use the same blood sample to conduct an additional T-Cell test by Roche (Elecsys® IGRA SARS-CoV-2 (20)) to compare the performance of the two diagnostic tests.

For this purpose we will collect 1 heparin blood sample (8 ml) from patients selected for this sub-sample. As these blood samples have to be processed within the same day we will only select patients from the study center Zürich and Basel for this blood sample. Heparin blood sample collected in Basel will be sent on the same day by bike carrier to the IMV in Zürich to assure that they are processed within the same day as they were collected.

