4. BACKGROUND AND RATIONALE

4.1 BACKGROUND AND RATIONALE

We have set up a COrona VaccinE tRiAL pLatform (COVERALL) nested into the existing prospectively collected data structure of the Swiss HIV Cohort Study (SHCS) and the Swiss Transplant Cohort Study (STCS), according to an adaptive trial **master protocol** (4). Within the frame of a **first sub-study** we have assessed in a head-to-head comparison the efficacy of BNT162b2 by Pfizer-BioNTech and mRNA-1273 by Moderna in immunocompromised patients form the SHCS and the STCS (5). In these patients the antibody response of mRNA-1273 was non-inferior to BNT162b2. Patients living with HIV had in general an antibody response, while a high proportion of transplant recipients had no antibody response. The **second sub-study** found similar results 8 weeks after the 3rd vaccination (i.e. non-inferiority of moderna vaccine; antibody response; *manuscript in preparation*).

The currently used SARS-CoV-2 vaccines were developed targeting the SARS-CoV-2 wild type and show limited efficacy against newer SARS-CoV-2 variants of concern. Hence, Moderna has developed a new bivalent booster vaccine based on variant spike sequences (Wuhan/Omicron BA.1). In a recent study this newly developed bivalent mRNA-1273.214 vaccine showed also a potent neutralizing antibody response against Omicron subvariants and a superior antibody response against alpha, beta, gamma, delta and omicron variants when compared to the approved monovalent vaccine mRNA-1273 Spikevax (6). Similarly, Pfizer-BioNTech has developed a bivalent mRNA vaccine (Wuhan/Omicron BA.1) with promising results (7, 8). Currently, evidence on the efficacy and safety of bivalent mRNA-vaccines in immunocompromised persons is very limited.

Hence, we propose a **third sub-study** of our COVERALL study assessing the humoral and cellular immune response, clinical and safety outcomes of the bivalent mRNA-vaccines (Wuhan/Omicron BA.1) in patients from the SHCS and STCS who have received at least three monovalent m-RNA SARS-CoV-2 vaccinations by either Moderna or Pfizer-BioNTech. Little is known about the cellular (T-cell mediated) immune response for these bivalent vaccines. Evidence from previous mRNA vaccine studies has shown inconsistent patterns between humoral and cellular response, especially among solid organ transplant recipients (9-11).

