13.3.2 Analyses of immunological and clinical outcomes

Descriptive statistics will be used to present immunological and safety outcomes. We will report frequency and percentage with 95% Wald confidene interval (CI) of positive immune response and

geometric mean titer (GMT) with 95% CI. GMT are defiened as the anit-logs of the means and addressed anticipated right-skewness of the data. Safety outcomes will be reported as frequency and percentage with 95% CI. For scenario 1, we will additionally report mean difference in positive response and ratio of GMT between the two bivalent vaccines with 95% CI.

Baseline and demographic characteristics will be summarised overall and -for scenario 1 – by vaccine received.

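### Baseline S antibody is drawn in previously vaccinated patients, but no antibody endpoint or analysis uses it, so response to the bivalent dose is not separated from carry-over

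*Protocol*

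**What the plan says.** The rationale (protocol section 4.1) describes the bivalent sub-study as being "in patients from the SHCS and STCS who have received at least three monovalent m-RNA SARS-CoV-2 vaccinations". The exclusion criteria in section 7.4 set a lower floor: they remove only patients without basic immunisation, exemplified as "two shots of Spikevax from Moderna, two shots of Comirnaty from Pfizer-BioNtech". On either description every participant has been vaccinated before, and no criterion excludes someone already above an antibody threshold.

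The study schedule (synopsis and section 10) places the Elecsys S and N tests at baseline, 4 weeks, 8 weeks and 6 months. Section 10.1.1 confirms the pre-dose measurement, "We will also assess antibody response at baseline (i.e. before vaccination with bivalent SARS-CoV-2 vaccine"), and then notes that some patients may already have had the bivalent vaccine, "hence we will not have a baseline blood sample from those patients".

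The antibody endpoints in section 6.4.1 are:
- the proportion with a positive response, qualified by "An antibody response will be considered to be still sufficient, using the threshold ≥100 units/ml";
- "Geometric mean of quantitative antibodies against RBD at 4 weeks, 8 weeks, and 6 months using Elecsys S test from Roche";
- the proportion at or above the manufacturer's 0.8 units/ml cut-off at the same three visits.

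Section 13.3.2 plans percentages with Wald intervals, "geometric mean titer (GMT) with 95% CI" and, in Scenario 1, a difference in positive response and a GMT ratio between vaccines. Baseline appears there only as a summary of baseline characteristics. The first objective, in both scenarios, is to assess the efficacy of the booster. Scenario 2 has a single arm.

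**The concern.** A booster study in previously vaccinated people has to distinguish the antibody a patient brings from the antibody this dose adds. An absolute post-dose value mixes the two. A patient at or above the cut-off before and after the dose counts as a responder whether the titre rose tenfold or not at all, and a high post-dose GMT may partly reflect earlier doses or past infection.

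In Scenario 2 there is no comparator, so the patient's own pre-dose value is the only reference the study holds. In Scenario 1 the comparison is not randomised, the second arm may open up to three months after the first, and the planned mix differs: transplant recipients are 60 of 160 (37.5%) in the Moderna arm and 20 of 80 (25%) in the Pfizer-BioNTech arm. An unadjusted GMT ratio carries any difference in baseline titre between the arms.

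The effect is probably uneven across strata. Section 4.1 reports from the earlier sub-studies: "Patients living with HIV had in general an antibody response, while a high proportion of transplant recipients had no antibody response". Carry-over is therefore likely to be largest in the HIV strata (100 of 160 participants in Scenario 2; 160 of 240 in Scenario 1) and smaller in transplant recipients.

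**Working it through.** **The plan's own figures.** Section 13.1 gives convenience samples of 160 and 240, with no power calculation. The strata add up: 30 + 30 + 50 + 50 = 160; 10 + 10 + 30 + 30 = 80; 160 + 80 = 240.

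**What a threshold proportion can distinguish.** Let p0 be the share at or above the threshold before the dose and c the share of the remainder that crosses it after the dose. Assume nobody already above falls below by the visit in question. The reported proportion is

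P = p0 + (1 − p0) × c,

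and the share of counted responders who were already above is p0 / P. The documents give no value for p0 or c, so the values below are assumptions. N = 160 (Scenario 2). The Wald interval is P ± 1.96 × √(P(1 − P)/160).

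| Assumed p0 | Already above, of 160 | Able to cross, of 160 | Wald 95% CI if c = 0 | P if c = 0.5 | Already above among responders, c = 0.5 |
|---|---|---|---|---|---|
| 50% | 80 | 80 | 42.3 to 57.7% | 75% | 67% |
| 70% | 112 | 48 | 62.9 to 77.1% | 85% | 82% |
| 80% | 128 | 32 | 73.8 to 86.2% | 90% | 89% |
| 90% | 144 | 16 | 85.4 to 94.6% | 95% | 95% |
| 95% | 152 | 8 | 91.6 to 98.4% | 97.5% | 97% |

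One observed result, 90%, is compatible with very different effects:
- p0 = 90%, c = 0: 0.90 + 0.10 × 0 = 0.90
- p0 = 80%, c = 0.5: 0.80 + 0.20 × 0.5 = 0.90
- p0 = 50%, c = 0.8: 0.50 + 0.50 × 0.8 = 0.90

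The proportion alone does not tell these apart; p0 in the same participants does.

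**What a baseline GMT adds.** For the same n participants, log(follow-up GMT) − log(baseline GMT) equals the mean of the individual log changes. The ratio of the two GMTs is then exactly the geometric mean fold rise, and pairing affects only the confidence interval. If the follow-up GMT covers everyone and the baseline GMT covers only those with a pre-dose sample, the ratio compares different sets of people.

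**Precision of the proposed summary.** The 95% limits of a geometric mean fold rise are the estimate multiplied and divided by 10^(1.96 × SD/√n), where SD is that of the within-patient log10 change. The documents give neither the SD nor the share with a baseline, so both are assumed.

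| n with baseline | SD 0.3 | SD 0.5 | SD 0.8 |
|---|---|---|---|
| 160 (all) | 1.11 | 1.20 | 1.33 |
| 120 (75%) | 1.13 | 1.23 | 1.39 |
| 80 (50%) | 1.16 | 1.29 | 1.50 |
| 50 (full HIV stratum) | 1.21 | 1.38 | 1.67 |
| 30 (full transplant stratum) | 1.28 | 1.51 | 1.93 |

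Even with half the baselines missing, the overall fold rise would be estimated to within a factor of 1.5 under these assumptions.

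**The case against.** The strongest reply is that the information is not lost. S antibody is scheduled at baseline and at every visit, and a descriptive plan may well tabulate it. A reader might infer from the endpoint list that Scenario 2 is unable to reveal anything about the booster's effect. The documents do not support that: what is missing is a named summary, not the data.

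Second, a reader might conclude that the 100 units/ml endpoint is wrong. It is not. Its wording concerns whether antibody is still sufficient for protection, and a patient above 100 both before and after is correctly counted in that sense. The difficulty arises only when the same proportion is read as a response to this dose or as booster efficacy.

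Third, it would be too strong to say that a baseline GMT beside the follow-up GMT does not help. In the same participants it gives the fold-rise point estimate.

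Fourth, section 13 declares the study exploratory, with no hypothesis and no decision rule. This lowers the stakes, but a descriptive summary should still describe the stated objective. Sections 13.3.1 and 13.4 defer to a master protocol that is not among the documents. Section 13.3.2 sets out its own analyses and does not defer.

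Finally, an uncontrolled before-after change is itself mixed with new infection and monoclonal antibody use. That stands and limits what any fold rise can claim. Both are recorded during follow-up, so their influence can be examined.

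**Conclusion.** The point holds for the antibody endpoints and their analysis as written: baseline S antibody is collected, and no endpoint or analysis in sections 6.4.1 and 13.3.2 uses it to describe response to the bivalent dose. It weighs most on the efficacy objective in Scenario 2 and probably most in the HIV strata; in Scenario 1 it leaves a non-randomised GMT ratio unadjusted for baseline titre.

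Its numerical size is unknown, because the documents give no baseline proportion, no SD of titre change and no share of participants with a pre-dose sample. The figures above show what is possible under stated assumptions. A reader might also look for a fixed gain in precision from pairing. None can be claimed, because the plan contains no unpaired change to compare with and not everyone will have a baseline.

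The safety endpoints are not affected. The T-cell objective mentions build-up and has a baseline test, but no analysis is defined for it; it is outside this point. Given the exploratory aim, this is an amendment worth making before analysis, not a flaw that invalidates the study.

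**What to change.** Keep the planned endpoints, and describe the 100 units/ml proportion as protection status. Add to sections 6.4.1 and 13.3.2, for participants with a pre-dose sample:

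1. The geometric mean fold rise from baseline to 4 weeks, 8 weeks and 6 months with a paired 95% CI, overall and by the four strata.
2. Baseline GMT and the baseline proportions at or above 0.8 and 100 units/ml, in the same participants as the follow-up values set beside them.
3. Optionally, as description only, the proportion reaching 100 units/ml among those below it at baseline, with a note that selecting on a low value invites regression to the mean.
4. In Scenario 1, a GMT ratio adjusted for baseline log titre, beside the planned unadjusted ratio in all participants.
5. A statement that the before-after change is uncontrolled, with the fold rise repeated after excluding participants with new infection (including N-antibody evidence) or monoclonal antibody use.

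Report how many participants in each stratum and arm have a baseline sample.

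The cost is analysis wording and programming; no additional visit or blood draw is needed. The drawback is that these summaries cover only participants enrolled before the bivalent dose. That group may differ from the rest, its share may differ between arms, and some Scenario 1 transplant strata have only 10 planned participants, so their estimates will be imprecise.
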